## **ABBREVIATIONS**

AE	Adverse event
ATC	Acute traumatic coagulopathy
CDC	Centers for Disease Control and Prevention
CONSORT	CONsolidated Standards of Reporting Trials
DSMC	Data Safety and Monitoring Committee
DVT	Deep vein thrombosis
GOSE	Glasgow Outcome Scale Extended
IEAC	Independent Endpoints Adjudication Committee
ITT	Intention-To-Treat
NHMRC	National Health and Medical Research Council
PI	Principal Investigator
SAE	Serious Adverse Event
SD	Standard deviation
SSI	Surgical site infection
ТХА	Tranexamic acid
WHODAS	World Health Organisation Disability Assessment Schedule 2.0, 12 item

# **Study synopsis**

## Study design

Prospective, multi-centre, randomised, double-blind, placebo-controlled trial.

## Study hypothesis

TXA given early to injured patients who are at risk of acute traumatic coagulopathy (ATC) and who are treated in advanced trauma systems reduces mortality and improves recovery at 6-months after injury.

## Primary Objective:

To determine the effect of early administration of tranexamic acid (TXA), compared to placebo, on mortality and favourable outcomes (moderate disability or good recovery) at six months in severely injured adults at risk of ATC who are treated in advanced trauma systems.

## Secondary Objectives:

(1) To determine the effect of early administration of TXA, compared to placebo, on coagulation and fibrinolysis, and on clinical outcomes that are mediated through other putative inflammatory, immune, and neurological effects of plasmin.

(2) To determine whether early administration of TXA, compared to placebo, is associated with excessive vascular occlusive events, especially among potentially higher risk patients (e.g., aged >50 years old).

## Inclusion criteria

- Adult patients (aged  $\geq$ 18 years).
- Injury through any mechanism.
- Coagulopathy of Severe Trauma score  $\geq$ 3.
- First dose of study drug can be administered within 3 hours of injury.
- Patients to be transported to a participating trauma centre.

## **Exclusion criteria**

- Suspected pregnancy.
- Nursing home residents.
- Age <18 years.

Further details of the trial design are available in the published PATCH protocol paper. (1)

# **Outcome Definitions**

## **Primary outcome**

Dichotomised Glasgow Outcome Scale Extended (GOSE) at 6 months: A favourable outcome is defined as GOSE scores 5-8 (moderate disability or good recovery) as opposed to GOSE scores 1-4 (died=1, severe disability 2-4).

# Secondary outcomes

- 1. Units of blood products used (packed red blood cells, fresh frozen plasma, platelets, prothrombin complex concentrate, recombinant factor VIIa, cryoprecipitate) in the first 24 hours
- 2. Blood lactate concentration at patient arrival to hospital
- **3.** Coagulation profile (international normalised ratio, activated partial thromboplastin time, fibrinogen, platelet count) at:
  - a. hospital arrival;
  - b. end of treatment with study drug (i.e., immediately after administering the second dose of the study drug by 8-hour infusion);
  - c. 24 hours after the first dose of study drug.
- **4.** Vascular occlusive events (deep venous thrombosis, pulmonary embolism, myocardial infarction, stroke) up until 28 days or hospital discharge (whichever occurs first).
- 5. Ventilator-free days in first 28 days.
- 6. Mortality at:
  - a. 24 hours;
  - b. 28 days;
  - c. 6 months.
- 7. Proportion of deaths due to:
  - a. bleeding;
  - b. vascular occlusion (pulmonary embolus, stroke or acute myocardial infarction);
  - c. multiorgan failure;
  - d. brain/neurological injury.
- **8.** Cumulative incidence of sepsis up until 28 days or hospital discharge (whichever occurs first).
- **9.** Quality of life (World Health Organisation Disability Assessment Schedule (WHODAS) 2.0 and EuroQol 5-Dimension (EQ-5D)) at 6 months.

## Randomisation

Trial packs are prepared by an independent pharmaceutical packaging company with either TXA or placebo. Packs are consecutively numbered, opaque, foil parcels with a tamper proof seal. Upon confirmation of eligibility, patients are randomised (1:1) to TXA or placebo, with the randomisation stratified by state and country participating in the study, and additionally by the presence of severe traumatic brain injury (TBI) defined by a Glasgow Coma Scale (GCS) <9 assessed at the time of randomisation.

## **Interim Analyses**

Two planned interim safety analyses for potential harm have been performed by the independent data and safety monitoring committee (DSMC) at 25% and 50% patient enrolment. Both analyses examined in-hospital and 28-day mortality using the Haybittle-Peto conventional 3-SD threshold of a standardised statistic (ie, |Z|>3), corresponding to two-tailed p-value of 0.003. Based on the observed effects of the study drug and adherence to the study protocol in these analyses, the members of the DSMC were unanimous in recommending to the management committee continuation of the study to full enrolment.

# Sample size

Targeting 90% power to detect an increase in a favourable GOSE outcome (scored 5–8) from 60% to 69% with TXA, this trial would require 592 patients in each arm (1184 total) with a twosided 5% significance level. In a protocol amendment (PATCH Protocol ANZIC-RC/ V.1.6 3 February 2020) accommodation for a 10% loss to follow-up, the required sample size was increased to 658 patients in each arm (1316 total).

# STATISTICAL ANALYSES

# **General principles**

The analysis and reporting of the results will follow the CONSORT guidelines. (2) Baseline characteristics will be tabulated by using appropriate summary statistics. Data for the primary outcome will be analysed using the intention-to-treat (ITT) and per protocol (PP) populations (see definitions and details below), with the ITT analysis regarded as the principal analysis. All secondary and tertiary outcomes will be analysed using the intentioe using the ITT population only. A nominal two-tailed 5% significance level will be employed. No adjustment to the 5% level is required for the two interim analyses due to their conservative boundaries having negligible impact on the overall Type I error rate. No correction for multiple testing will be performed.

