# **Analysis Populations**

## A. Intention-To-Treat (ITT) population

The ITT population will consist of all randomised patients.

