## B. Per Protocol (PP) population

The PP population will consist of all randomised patients with the exception of those who did not receive both doses of study drug or received open label TXA or did not meet the inclusion/exclusion criteria: age <18 years, had a COAST score <3, received their study drug >3 hours after injury, were pregnant, were residents at an aged care facility or did not attend a participating study centre.

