# Secondary and tertiary endpoint analyses

The binary secondary outcomes of vascular occlusive events (#4), mortality at 24 hours, 28 days and 6 months (#6) and incidence of sepsis to 28 days (#8) will be analysed using the same log-binomial regression modelling approach as the primary outcome. Cumulative mortality to 6 months will also be displayed with Kaplan-Meier curves. Blood product usage (#1) will be dichotomised as any/none and also analysed with log-binomial regression. The quantity of blood product usage among patients receiving the product will be summarised with medians and interquartile ranges, and compared between treatment groups using quantile (median) regression, reporting the difference in medians between treatment arms together with 95% Cls and p values. Analyses of blood lactate concentration (#2) (regardless of assay method) and coagulation profile variables at each time point (#3) will similarly use quantile regression to compare medians between treatment groups. Blood lactate concentration (#2) obtained by venous and arterial samples will each also be dichotomised at >3mmol, and a composite measure of >3mmol for either sampling method will be calculated. INR (#3) will be dichotomised at >1.3 IU, and fibrinogen (#3) at <1 g/L and at <2 g/L. These dichotomised variables will be analysed as binary variables as above. Ventilator-free days in the first 28 days (#5) will assign a value of 0 to patients dying within 28 days regardless of location at time of death, and a value of 28 days if never ventilated in ICU or never admitted to ICU. This will be analysed using quantile regression to estimate the difference in median ventilation-free days. The 4 causes of death (#7a,b,c,d) in patients that died at any time up to 6 months will be tabulated and reported descriptively. The cumulative incidence of each cause of death to 6 months will be displayed graphically taking into account the other competing causes of death, and with cause-specific hazard ratios estimated using Cox regression with censoring at the time of all other causes of death. A composite cause of 'potentially preventable death' will be calculated as any of bleeding, vascular occlusion and multi-organ failure. Comparison of median quality of life outcomes at 6 months (#9) between treatment arms will be analysed using quantile regression, with patients not alive at 6 months treated as having missing values (and see below), and with EQ-5D calculated using Australian weights (3).

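### Vascular occlusive events, the harm named in secondary objective 2, have no exposure-based analysis beside ITT, although missed doses and open-label TXA are foreseen and could dilute an excess

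*SAP*

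**What the plan says.** Secondary objective 2 is a harm question: whether early TXA, compared with placebo, "is associated with excessive vascular occlusive events, especially among potentially higher risk patients". The endpoint is secondary outcome 4: "Vascular occlusive events (deep venous thrombosis, pulmonary embolism, myocardial infarction, stroke) up until 28 days or hospital discharge", whichever comes first.

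General principles gives the primary outcome two populations, ITT and per protocol, and restricts all other outcomes to one. The sentence opens "All secondary and tertiary outcomes will be analysed using" and is garbled in the middle, but its end is clear: "using the ITT population only". The ITT definition carries no dosing condition: "The ITT population will consist of all randomised patients".

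The per-protocol definition removes, among others, "those who did not receive both doses of study drug or received open label TXA". The SAP uses this population for GOSE only. It defines no safety, any-dose or as-treated population.

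Under Secondary and tertiary endpoint analyses, outcome 4 is compared by a log-binomial risk ratio. A further analysis uses cumulative incidence with death as a competing risk. Neither changes the population.

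**The concern.** Non-receipt and contamination matter differently for benefit and for harm. For a claim of benefit, the dilution they cause under ITT makes the claim harder to reach, which is conservative. For a harm it runs the other way: a real excess looks smaller and is more easily missed.

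The SAP treats departures from assigned treatment as important enough for a second analysis of GOSE, but not for the one harm that has its own objective. Because secondary outcomes are restricted to ITT only, an exposure-based set defined in the protocol, which is not shown, would not be used for this outcome as the SAP is written.

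At stake is how a near-null ITT result would be read under objective 2. Without any view of the outcome by exposure, readers could not judge how far dilution contributed to it.

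**Working it through.** **1. The plan's own figure.** The SAP states no figure for vascular occlusive events, so the only one to reproduce is the sample size. With 60% against 69%, two-sided 5%, 90% power and pooled variance under the null:

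n = [1.960·√(2·0.645·0.355) + 1.2816·√(0.60·0.40 + 0.69·0.31)]² / 0.09² = 592 per arm

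592 / (1 − 0.10) = 657.8, so 658 per arm. Both figures agree with the SAP and are not in dispute. The checks below use 658 per arm.

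**2. Dilution model.** The inputs here are assumptions, because the SAP gives none of them:
- p: risk without TXA
- RR: true risk ratio in the exposed
- u: share of the TXA arm that receives no study drug
- c: share of the placebo arm given open-label TXA

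ITT risk, TXA arm = (1 − u)·p·RR + u·p

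ITT risk, placebo arm = (1 − c)·p + c·p·RR

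Power comes from the two-sided 5% Wald test of the log risk ratio, with SE = √[(1 − p₁)/(n₁p₁) + (1 − p₀)/(n₀p₀)].

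The model takes undosed patients to carry the placebo risk, open-label TXA to carry the full risk of study TXA, and departures to be unrelated to baseline risk.

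**3. One case in full** (p = 0.15, RR = 1.40, u = 0.10, c = 0.20):
- TXA arm: 0.90·0.21 + 0.10·0.15 = 0.204
- Placebo arm: 0.80·0.15 + 0.20·0.21 = 0.162
- Risk ratio: 0.204 / 0.162 = 1.26
- SE = 0.117 and log ratio = 0.2305, so z = 1.96 and power = 50%

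**4. Range.**

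| p | true RR | u | c | ITT RR | power |
|---|---|---|---|---|---|
| 15% | 1.40 | 0 | 0 | 1.40 | 80% |
| 15% | 1.40 | 5% | 5% | 1.35 | 72% |
| 15% | 1.40 | 5% | 10% | 1.33 | 67% |
| 15% | 1.40 | 10% | 20% | 1.26 | 50% |
| 20% | 1.30 | 0 | 0 | 1.30 | 73% |
| 20% | 1.30 | 5% | 5% | 1.27 | 64% |
| 20% | 1.30 | 5% | 10% | 1.25 | 59% |
| 20% | 1.30 | 10% | 20% | 1.20 | 44% |

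A separate check with a two-proportion test gives the same picture. At p = 10% and RR 1.50, power is 78% undiluted and 59% with u = c = 10% (ITT RR 1.38).

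**5. What an any-dose population recovers.** Restricting to patients who received any study drug, grouped by the pack given, sets u to 0 but leaves c as it was. Both arms are taken to shrink equally, by the share u. At p = 0.15, RR = 1.40:
- u = 5%, c = 10%: 0.21 / 0.156 = 1.35, up from 1.33; power 69%, up from 67%
- u = 10%, c = 20%: 0.21 / 0.162 = 1.30, up from 1.26; with 592 per arm, power 56%, up from 50%, against 80% undiluted

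Most of the loss in these cases comes from contamination, which this population does not touch.

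**The case against.** The strongest reply is that ITT is a legitimate answer to objective 2, which asks about early administration of TXA compared with placebo. The SAP reports a risk ratio with a 95% confidence interval and adds a competing-risk analysis. It has no rule that a non-significant result means no harm. All of this stands. ITT should remain the main analysis, and the SAP does not contradict itself here.

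A reader might infer from the per-protocol definition that many patients will receive no study drug at all. The text does not show this. It excludes patients who missed either dose, which includes those who had the first dose but not the second, and they are exposed. Nor does it say that open-label TXA will go mainly to the placebo arm. The shares u and c are therefore assumptions, and the model leaves out open-label TXA in the TXA arm. If open-label use carries less risk than the study regimen, the dilution is smaller.

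Any exposure-based comparison also has its own bias. Receipt of open-label TXA is a post-randomisation event that may depend on the patient's condition and assigned arm. Counting it as exposure invites confounding; stopping follow-up at that point may censor informatively. Such an analysis should not be able to overrule the randomised one, which rules out requiring the two to agree before any conclusion is drawn.

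What survives is the direction of the dilution for a harm, and the lack of any planned view of this outcome by exposure.

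**Conclusion.** The point holds as a case for a supplementary analysis, not as an error in the main one. If TXA raises the risk of vascular occlusive events, wholly undosed TXA-arm patients and contaminated placebo patients both pull the ITT risk ratio toward 1, and the SAP as written allows no other population for this outcome.

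The size depends on rates that the SAP does not give. It is modest at 5% of each kind of departure and material when departures reach 10% to 20%. The figures hold only under the model's assumptions of equal risk from open-label and study TXA and departures unrelated to baseline risk.

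A stronger reading would be that the planned analysis cannot distinguish no harm from diluted harm. The documents do not support that: the confidence interval still shows which effects of assignment are compatible with the data, and the amount of dilution is unknown and may be small.

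**What to change.** Keep ITT as the main analysis of every secondary outcome. For outcome 4 only:

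1. In General principles and Analysis Populations, define a supplementary population of patients who received any study drug, grouped by the pack given. Repeat the planned log-binomial and competing-risk analyses in it.
2. Report, by arm, how many patients received no study drug and how many received open-label TXA.
3. Because the any-dose set leaves contamination in place, add one labelled sensitivity analysis that accounts for open-label TXA, for example by counting it as exposure. State that it is not protected by randomisation and may be confounded or, if follow-up is cut at open-label use, informatively censored.
4. Interpret these results beside the ITT estimate and its confidence interval, with no rule that they must agree.

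The existing per-protocol set is a poor substitute. It requires both doses, the second an 8-hour infusion, and so removes patients who die or deteriorate early.

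The cost is a few lines of SAP text and reruns of models already planned. Dosing and open-label status are already needed for the per-protocol set; a time-based version of the sensitivity analysis would also need the time of open-label TXA. The downside is a little extra analysis and a supplementary comparison that randomisation does not fully protect.

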# **Analysis Populations**

## A. Intention-To-Treat (ITT) population

The ITT population will consist of all randomised patients.

## B. Per Protocol (PP) population

The PP population will consist of all randomised patients with the exception of those who did not receive both doses of study drug or received open label TXA or did not meet the inclusion/exclusion criteria: age <18 years, had a COAST score <3, received their study drug >3 hours after injury, were pregnant, were residents at an aged care facility or did not attend a participating study centre.

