#### Per Protocol analysis

The Per Protocol analysis will use the same methods as the ITT analysis, confined to the patients meeting the per protocol population definition. Because the patients not meeting the PP population definition have been excluded, there may no longer be balance in patient characteristics between treatment groups. The baseline characteristics in the TXA and placebo arms will be tabulated and compared for the 'compliant' (PP) patients. Any variables exhibiting imbalance will be adjusted for as covariates in the risk-ratio regression models.

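### The per-protocol definition has no exemption for patients who die before the second dose, so it removes unfavourable primary outcomes and can bias the per-protocol risk ratio

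*SAP*

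**What the plan says.** The per-protocol (PP) population is everyone randomised, "with the exception of those who did not receive both doses of study drug or received open label TXA", and also without those who breached listed eligibility criteria (SAP, B. Per Protocol (PP) population). The definition does not mention death.

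Four other places in the SAP matter here:

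- **Timing of the doses.** The first dose belongs to the first hours after injury: "First dose of study drug can be administered within 3 hours of injury" (Inclusion criteria). The second comes later and takes hours to give. The end-of-treatment coagulation sample is timed "immediately after administering the second dose of the study drug by 8-hour infusion" (Secondary outcomes, item 3b).
- **Death in the primary outcome.** A favourable GOSE is scored 5 to 8, "as opposed to GOSE scores 1-4 (died=1, severe disability 2-4" (Primary outcome).
- **PP method.** "The Per Protocol analysis will use the same methods as the ITT analysis, confined to the patients meeting the per protocol population definition" (Per Protocol analysis). The section accepts that balance between arms may be lost, and its remedy is: "Any variables exhibiting imbalance will be adjusted for as covariates in the risk-ratio regression models".
- **Status of the analysis.** Both populations are used for the primary outcome, "with the ITT analysis regarded as the principal analysis", and secondary and tertiary outcomes use ITT only (General principles).

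**The concern.** A patient who receives the first dose and dies before the second is begun has not received both doses, so the rule as written excludes that patient. The same death is an unfavourable primary outcome. For these patients, the event that defines failure is also the reason for leaving the analysis.

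This has two consequences. Favourable proportions are inflated in any arm that has such deaths. And if treatment changes the number of early deaths, the two arms lose different numbers of failures and the PP risk ratio no longer estimates the treatment effect. The study hypothesis is that TXA reduces mortality, and mortality at 24 hours is a secondary outcome, so a difference in early deaths is something the trial itself allows for.

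The planned remedy does not address this. Adjusting for baseline variables cannot restore deleted failures, and in general cannot remove selection on a post-randomisation event that is part of the outcome.

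The SAP deals with death explicitly elsewhere: patients who die within 28 days get zero ventilator-free days, death is a competing risk for vascular events and sepsis, and the quality-of-life analyses either impute values for death or weight for truncation by it. The PP definition has no comparable provision.

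**Working it through.** **Design figure first.** Inputs from Sample size: favourable outcome "from 60% to 69% with TXA", 90% power, two-sided 5%, 1:1 allocation.

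n per arm = [1.960 × √(2 × 0.645 × 0.355) + 1.2816 × √(0.60 × 0.40 + 0.69 × 0.31)]² / 0.09² = 592. Allowing for 10% loss, 592 / 0.90 = 657.8, so 658. Both match the SAP and are not in dispute. The design risk ratio is 0.69 / 0.60 = 1.15.

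**Effect of the exclusion.** Let d be the share of an arm that dies before the second dose, and suppose there are no other exclusions. None of these patients has a favourable outcome, so only the denominator shrinks:

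- PP favourable proportion = ITT favourable proportion / (1 − d)
- PP risk ratio = ITT risk ratio × (1 − d_placebo) / (1 − d_TXA)

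The SAP gives no value for d. The shares below are assumptions, applied to the design effect.

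| d placebo / TXA | PP favourable, placebo | PP favourable, TXA | PP risk ratio |
|---|---|---|---|
| 0 / 0 | 60.0% | 69.0% | 1.15 |
| 5% / 5% | 63.2% | 72.6% | 1.15 |
| 10% / 10% | 66.7% | 76.7% | 1.15 |
| 15% / 15% | 70.6% | 81.2% | 1.15 |
| 10% / 8% | 66.7% | 75.0% | 1.125 |
| 5% / 2% | 63.2% | 70.4% | 1.115 |
| 10% / 5% | 66.7% | 72.6% | 1.09 |
| 15% / 10% | 70.6% | 76.7% | 1.09 |
| 15% / 6% | 70.6% | 73.4% | 1.04 |

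Equal shares inflate the proportions but leave the risk ratio alone. Fewer early deaths on TXA pull the PP risk ratio below 1.15.

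**No overall effect on the primary outcome.** Take 60% favourable in both arms and early deaths of 10% on placebo and 5% on TXA, so that the early deaths averted become later unfavourable outcomes. PP gives 0.60 / 0.90 = 66.7% v 0.60 / 0.95 = 63.2%, a risk ratio of 0.95 where the ITT value is 1.00.

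**With the exemption.** If these deaths stay in and there are no other exclusions, the PP risk ratio equals the ITT value, 1.15 at the design effect.

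**The case against.** The strongest reply is that little depends on this. ITT is the principal analysis and includes everyone randomised, PP is applied to the primary outcome only, and mortality at 24 hours, 28 days and 6 months is analysed by ITT, where early deaths remain visible. Nothing in the SAP makes the trial's conclusion depend on PP. That stands, and it limits the severity. It does not remove the fault: PP is the only other analysis population named for the primary outcome, and it will carry its own risk ratio, confidence interval and p-value.

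A reader might also infer more than the SAP supports:

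- *That the outcome decides PP membership in general.* It does so only for deaths before the second dose. Later deaths and survivors with severe disability are not removed by this rule.
- *That deaths during the infusion are certainly excluded.* The SAP does not say whether a partly given infusion counts as received, and the 8-hour wording comes from the timing of a blood sample. These deaths are ambiguous.
- *That excluding recipients of open-label TXA selects on bleeding.* This is plausible, but the SAP does not say why open-label TXA would be given.
- *That PP would erase a real benefit.* If all the benefit comes from averting early death, and patients reaching the second dose do equally well in both arms, the PP risk ratio is 1.00 by identity. With early deaths of 10% v 5%, ITT is 60.0% v 63.3% (risk ratio 1.06) and PP is 66.7% in both. That follows from the assumption. At the design effect, the assumed shares give attenuation.
- *That PP would manufacture a benefit.* By this route alone, that would need more early deaths on TXA than on placebo, the opposite of the hypothesis.

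**Conclusion.** The point holds as a moderate issue in a supporting analysis. As written, the PP rule removes patients who die before the second dose, all of whom are primary-outcome failures, and the planned covariate adjustment cannot put that right. The direction needs no outside figure: favourable proportions are inflated wherever such deaths occur, and the risk ratio is biased when their shares differ by arm.

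The size is conditional. At the design risk ratio of 1.15, with no other exclusions, the five unequal pairs of assumed early-death shares give PP risk ratios of about 1.04 to 1.13, and equal shares give no bias in the ratio. The true shares are not in the SAP. The sample size, the principal ITT analysis and all secondary outcomes are untouched, so it would be wrong to read this as a threat to the trial's main conclusion.

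**What to change.** Amend section B of Analysis Populations in three respects:

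1. Otherwise compliant patients who received the first dose and died before the second was started or completed stay in the PP population. The requirement for both doses then applies to patients who lived long enough to receive them.
2. State, for analysis purposes, whether a partly given infusion counts as the second dose received.
3. Report PP exclusions by arm and by reason.

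The cost is a sentence or two of SAP text and a little programming, provided dose and death times are recorded. The downside is that the PP set will include some patients who received only part of the treatment; the counts by arm will show how many.

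Weighting for adherence or a complier-average estimate could be added, but is not needed to repair this fault. The latter has a difficulty of its own: a patient given only the first dose has still had active drug, so the usual exclusion restriction is doubtful if compliance means both doses.
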